8.1.2.2 Optivate[®] Recovery Over Time

For V1 (1 ED), V2 (10-15 ED), V3 (50-75 ED) and V4 (100 ED) recovery will be calculated using the formula in 8.1.2.1. An overall Optivate[®] recovery value will be calculated across the whole study and for each batch on a per subject basis. An ANOVA will also be performed to compare recovery values at V1, V2, V3, and V4 and across batches.

8.1.2.3 Optivate[®] Therapy to Treat Break Through Bleeds

The following will be assessed:

- 1. The number of break-through bleeds including:
 - a. severity (major, minor, emergency)
 - b. duration
 - c. location (joint, muscle, open/other)
 - d. cause (spontaneous, injury, other).
- Clinician's judgement of break-through bleed treatment outcome (Excellent, Good, Moderate, Poor).
- 3. Subject's judgement of break-through bleed treatment outcome (very helpful, helpful, helpful, helped a little, did not help).

8.1.2.4 Overall Consumption of Optivate[®]

- 1. Number of exposure days for each subject and per month/subject, per year/subject and overall.
- 2. Total dose in IU/kg of Optivate[®] and average dose per infusion for prophylactic use, to treat a bleed, any additional preventative use and overall use; all analysed on a per subject basis.
- 3. Total number of infusions for prophylactic use, to treat a bleed, any additional preventative use and overall use; all analysed on a per subject basis.
- 4. Mean dose in IU/kg of FVIII per subject/month and per subject/year prophylactically, to treat a bleed, any additional preventative use and overall use; all analysed on a per subject basis.
- 5. Mean number of infusions per subject/month and per subject/year for prophylactic use, to treat a bleed, any additional preventative use and overall use; all analysed on a per subject basis.

For calculation purposes, a month will be defined as 28 days and a year will be defined as 365 days. Where a subject has completed less than a year of Optivate[®] treatment, the data will be extrapolated to calculate the per consumption per year.

8.1.2.5 Genotype Analysis

Genotype data will be collected at screening (also see Section 7.9.6) and the data on mutation type for each subject will be listed.

8.2 Safety Variables

All subjects who received at least one dose of Optivate[®] will be included into the safety population The following will be used to assess the safety of Optivate[®]:

- AEs, product-related AEs, serious ADRs
- Viral serology
- Physical/Medical examination.
- Inhibitor development (this is a safety measurement and will be accessed as a primary efficacy endpoint, see Section 8.1.1).

8.2.1 Adverse Events

All the adverse events data (from CRF and study diary) will be pooled together and reported in terms of the type, duration, treatment and/or severity. For further information on the definition and reporting of adverse events, see Appendix I.

All adverse events (product related or unrelated) that appear or worsen during the course of the study will be captured on the database. If an AE occurs at the study site this will be recorded in the CRF. If an AE occurs during home therapy this will be recorded in the study diary to avoid duplicate entry. This data will be pooled in the final analysis. If a subject has a recurring condition, whether related to FVIII deficiency or not, then this should be recorded at the Screening Visit in the Medical History pages of the CRF.

Fluctuations or re-occurrences of the condition, that are considered normal for the subject and are recorded in the medical history, need not be reported as an adverse event. However, if the condition were to deteriorate during the study this would then be recorded as an adverse event.

If surgery is planned before entry into the study, the indication for surgery should be recorded in the medical history, and this will not be reported as an adverse event, unless the planned hospitalisation is prolonged. Dosing during surgery should be as per the Optivate[®] SmPC¹ and Section 6.2.3. The use of antifibrinolytic agents is prohibited during the trial, however if these are necessary during surgery then this will be allowed. In such cases the exposure days during surgery

will be excluded from the Optivate[®] EDs calculations. Both the CRA and the Sponsor will need to be notified if antifibrinolytic agents are used. If an AEs is considered to be related to surgery or is a complication of surgery this will be specified on the AE the form. If the AE meets the definitions of a Serious Adverse Event (see Appendix I) this will be reported as a SAE. A narrative will be written for each surgical procedure.

A spontaneous bleed will not be reported as an adverse event, unless it represents a consistent worsening of factor VIII deficiency symptoms or the subject is hospitalised. Any excessive bleeding as a result of the surgery will be recorded as an AE. Bleed details will be recorded in the study diary and checked by site personnel.

8.2.2 CD4 Count

CD4 counts will be assessed by the Central Laboratory. Blood samples for CD4 count assessments will only be collected at the Screening Visit to assess subject's eligibility.

8.2.3 Viral Serology

Viral serology variables will be assessed by the central safety laboratory (see Section 7.9.5 for list of markers tested in the study). A blood sample to test for HIV will be collected at screening, to assess the subject's eligibility. Serum samples for all viral serology testing will be collected predose at the Baseline Visit (V1) and at the End-of-Study Visit (V4). Any changes in serology during the study period will be reported to the Sponsor immediately.

8.2.4 Physical/Medical Examination

A physical/medical examination including weight and height will be performed at the Screening Visit and the End-of-Study Visit (V4). The following body systems will be examined: HEENT, chest, cardiovascular, respiratory, abdomen, musculoskeletal, genito-urinal, skin and general appearance.

Any changes from the Screening Visit to the End-of-Study Visit (V4) will be recorded in the CRF. Any adverse change in the physical examination will be reported as an adverse event.

Body weight will also be recorded at all visits to allow for calculation of an exact dose in IU/kg.

9 SUBJECT WITHDRAWAL

Subjects may stop study treatment for any of the following reasons:

• Withdrawal of consent.

- Significant protocol deviation.
- Lost to follow-up.
- Incidental illness.
- Occurrence of adverse events (AEs) not compatible with the continuation of the subject's participation in the study, in the Investigator's opinion (*eg* anaphylactic or other severe/serious reaction to infusion, development of inhibitor).
- Investigator's request.
- Requirement for therapeutic intervention prohibited by the protocol *eg* FVIII containing product or antifibrinolytics agents (expect during surgery).
- Premature termination of the trial by BPL on account of an unacceptable risk-benefit ratio. If this occurs, BPL or BPL's representatives will notify the regulatory authorities, ethics committees and Investigators of the reason for premature study termination, within 15 days from the study being halted.
- Subject/guardian is unco-operative and non-compliant with respect to provisions of the protocol.
- Trial stopped by BPL as 10 evaluable subjects have 100 EDs with Optivate[®].
 NB:this may mean that the last two subjects enrolled into the study may receive a shorter treatment period.

The clinical Investigator may also remove a subject if, in his/her opinion, it is in the best interests of the subject.

Subjects are free to withdraw from the study at any time without providing reason(s) for withdrawal and without prejudice to further treatment. The reason(s) for withdrawal will be documented where possible, particularly where withdrawal is a consequence of an adverse event. The subject's primary care physician (where applicable) will be informed of the reason for withdrawal.

Data collected up until a subject's withdrawal from the study, including data for screen failures, will be retained on the clinical database and used in the analysis and clinical study report.

Subjects withdrawing from the study will be requested to complete the same final assessments as subjects completing the study according to the protocol, particularly safety assessments (see Section 7.4). If there is a medical reason for withdrawal, the subject will remain under the supervision of the Investigator until in satisfactory health or the subject's condition has stabilised.

Reasonable efforts will be made to contact subjects who are lost to follow-up. These efforts must be documented in the subject's medical records.

10. DATA ANALYSIS

10.1 Source Data

The collection and analysis of high quality data is dependent on accurate documentation in the subject's hospital notes, to allow accurate verification of CRF data. See Appendix II (Administrative Requirements) for more detail on the recording of data in subject's notes and maintenance of other study documents.

To avoid duplicate entry of AEs which occur at the study site these will be recorded in the CRF. AEs which occur during home therapy these will be recorded in the study diary.

10.2 Data Management and Coding

The CRO selected Data Management Group will be responsible for activities associated with the data management for the final analysis. This will include setting up a relevant database and data transfer mechanisms, along with appropriate validation of data and resolution of queries. Missing or inconsistent data will be queried in writing to the Investigator for clarification. Subsequent modifications to the database will be documented.

10.3 Statistical and Analytical plans

All tables, figures and listings will be produced using the most recent version SAS (Statistical Analysis System).

Unless otherwise stated, categorical data will be presented using counts and percentages, whilst continuous variables will be presented using the mean, 95% confidence interval for the mean, standard deviation (SD), median, minimum, maximum, number of subjects (n) and number of missing subjects or datapoints. Minima and maxima will be quoted to the number of decimal places as recorded in the CRF; means, and medians will be quoted to one further decimal place. SDs will be quoted to one further decimal place than the mean value. Percentages will be rounded to one decimal place.

The efficacy analysis will be performed for the per protocol population, and the safety population will be used to report all safety data, in accordance with the statistical analysis plan (SAP). Demographic data will be reported for the safety population.

All data will be listed. More information is in the SAP for the study.

10.4 Analysis Populations

The following analysis populations will be defined for this study.

If subjects suffering from severe haemophilia A with basal FVIII values of < 2% rather than < 1% are recruited into the study, in addition to the analysis for all subjects, two separate analyses will be conducted: One for subjects with a basal FVIII < 1%, the other for subjects with a basal FVIII < 2%.

Safety Population

The safety ITT population will be defined as all subjects who received at least part of one dose of Optivate[®]. Safety data will be analysed up to the point of withdrawal for subjects who withdraw, if the number of points is adequate to allow a scientific analysis.

Per Protocol Population

The per protocol population will be defined as all subjects who have completed a minimum of 100 EDs with Optivate[®].

NOTE: If antifibrinolytic agents have been administered during surgery, the surgery exposure days will not be included in the Optivate[®] ED calculations.

The efficacy analysis will include all the subjects in the per protocol population. The secondary analysis will include all subjects in the ITT population.

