7.5 Safety Follow-Up (FU) (telephone contact) – 28 days after last Optivate® infusion

Twenty-eight days after the last infusion of Optivate[®] the site staff will contact the subject by telephone to follow-up on any AEs. Any SAEs occurring within 28 days after the last dose of Optivate[®] will be reported according to procedures outlined in Appendix I.

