6.2. SAFETY POPULATION

The Safety Population is defined as all subjects who received at least part of one dose of Optivate[®]. The Safety Population will be used for all analyses of safety endpoints, and as a secondary population for the analysis of efficacy endpoints.

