7.3. MISSING DATA

All available data will be used in the statistical analysis. There will be no imputation for missing data.

Sponsor: BPL

Protocol: 8VWF07

Version: 1.0

Statistical Analysis Plan

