12. CHANGE FROM ANALYSIS PLANNED IN PROTOCOL

There are no changes to the analyses planned in the protocol.

Sponsor: BPL

Protocol: 8VWF07

Version: 1.0

Statistical Analysis Plan

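### Protocol 10.4 limits withdrawn subjects' safety data to the period before withdrawal and to cases judged adequate, in undeclared conflict with the SAP and with other protocol sections

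*Protocol*

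**What the plan says.** Protocol 10.4 defines the safety population by dosing alone, as "all subjects who received at least part of one dose of Optivate". The next sentence adds two limits for those who leave early. The first is a cut-off: "Safety data will be analysed up to the point of withdrawal for subjects who withdraw". The second is a condition: "for subjects who withdraw, if the number of points is adequate to allow a scientific analysis". Neither is explained further.

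Other parts of the plan carry no such limits:

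- Protocol 9 keeps the data collected up to withdrawal on the database and uses them in the analysis and the study report. It also asks withdrawing subjects to complete the final assessments.
- Protocol 10.3 uses the safety population to report all safety data, refers to the SAP for how this is done, and has all data listed.
- Protocol 10.7.1 sets the denominator for adverse event percentages as the number of subjects in the safety population.
- SAP 6.2: "The Safety Population will be used for all analyses of safety endpoints".
- SAP 7.3: "All available data will be used in the statistical analysis".
- SAP 7.4 places withdrawn subjects' final-visit data under the End of Study heading in Safety Population summaries.

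SAP 12 states: "There are no changes to the analyses planned in the protocol".

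**The concern.** Two rules stand for the same subjects, and the documents do not say that they differ. The protocol rule turns on a judgement that nobody is assigned to make and that is not fixed before the results are known.

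The direction of possible bias is plain. Protocol 9 gives severe infusion reactions and inhibitor development as examples of events that can lead to withdrawal. Subjects who leave early for these reasons tend to have the fewest measurements, so an adequacy test would bear most on them. Such a test also has little purpose for event data, since one adverse event is reportable however few visits the subject completed.

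The Safety Population summaries matter particularly here. A subject who withdraws before 100 exposure days is outside the Per Protocol Population (Protocol 10.4, SAP 6.1). The Safety Population tables are therefore the only summaries in which that subject can appear.

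**Working it through.** The plan states no figure on this point, so there is none to reproduce. The check compares the text, then illustrates the size.

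**Adequacy condition**

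| Source | Are withdrawn subjects' safety data used? | Condition on amount of data? |
|---|---|---|
| Protocol 10.4 | Yes, up to withdrawal | Yes, undefined |
| Protocol 9 | Yes, data collected up to withdrawal | None |
| Protocol 10.3 | All safety data reported; all data listed | None |
| SAP 6.2 | All safety analyses use the Safety Population | None |
| SAP 7.3 | All available data | None |
| SAP 7.4 | Withdrawal-visit data summarised | None |

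On the condition, Protocol 10.4 conflicts directly with every other row.

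**Cut-off at withdrawal**

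Data can exist after the withdrawal date:

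- Protocol 7.4 and 9 ask withdrawn subjects for the end-of-study safety assessments.
- Protocol 7.5 has a telephone contact 28 days after the last infusion and makes reportable "Any SAEs occurring within 28 days after the last dose of" Optivate.
- Protocol Appendix I, section 4 extends reporting beyond 28 days for serious events judged related.

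The SAP has no cut-off at withdrawal, and its definition of treatment-emergent events (SAP 10.2) has no end date. It does not mention post-withdrawal data by name. This part of the conflict therefore rests on the all-available-data rule, on SAP 7.4 and on the absence of a cut-off. It is less direct than the conflict over adequacy. Protocol 9 does not contradict the cut-off, because it speaks only of data collected before withdrawal.

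**Size, as an illustration**

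Assumptions: 12 subjects are dosed (the planned enrolment, Protocol 10.8), and one withdraws early with the only event of its kind. The denominator is the whole safety population (Protocol 10.7.1), so it stays at 12. Intervals are exact (Clopper-Pearson) at 95%.

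- Event included: 1/12 = 8.3%. Lower limit: 1 − 0.975^(1/12) = 0.2%. The upper limit solves (1 − p)^12 + 12p(1 − p)^11 = 0.025, giving p = 38.5%.
- Event left out of the summary: 0/12 = 0%. Upper limit: 1 − 0.025^(1/12) = 26.5%.
- With two such subjects: 2/12 = 16.7% (2.1% to 48.4%) against 0/12 (0% to 26.5%).

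**The case against.** The strongest reply is that the plan already leads to inclusion. Protocol 10.3 defers to the SAP for the reporting of safety data, and the SAP's working rules include every dosed subject. A statistician following the SAP would drop nobody. All data are listed (Protocol 10.3; SAP 7.1 is similar for relevant subject data), and serious events have their own listing (SAP 18). Confirmed inhibitors are reported as SAEs (Protocol 7.9.2). Inhibitor status is also the primary efficacy endpoint, summarised on both populations (SAP 9.1), so it is arguable whether the clause reaches it at all. The word points also reads more naturally as repeated measurements than as single events.

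Most of this stands, and it limits the point to summary tables. It does not remove the protocol sentence. It also does not square that sentence with SAP 12, which tells the reader that the two documents agree.

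Three stronger readings are tempting, and the documents support none of them:

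- A reader might infer that a withdrawn subject leaves the denominator, turning 1/12 into 0/11. Membership is set by dosing alone and Protocol 10.7.1 fixes the denominator, so the supported contrast is with 0/12.
- A reader might infer that the safety data would disappear from the record. Protocol 9 retains them and Protocol 10.3 lists them.
- A reader might infer that the 28-day follow-up events are excluded from analysis. Protocol 7.5 governs collection and reporting, and no SAP text excludes those events. Only a literal use of the Protocol 10.4 cut-off would do so.

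**Conclusion.** The inconsistency is real and undeclared. Protocol 10.4 contains an undefined condition, open to judgement after the data are seen, that no other part of the plan shares. Its cut-off also sits badly with the safety data that the protocol itself collects after withdrawal.

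The practical effect is limited. If the SAP is followed as written, the data are included. If the protocol sentence is applied instead, an event could be missing from a summary table while remaining in the listings. In the illustration above, that one decision would turn a table with an event into a table with none. The size depends on the assumed 12 dosed subjects and single early withdrawal; neither is a prediction. This is worth correcting in a small safety study, but it does not show that any data would in fact be lost.

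**What to change.** Delete the sentence on withdrawn subjects in the Safety Population paragraph of Protocol 10.4. In its place, state: *All available safety data from every subject who received any Optivate will be summarised and listed, whatever the amount, including baseline, withdrawal-visit and follow-up data and any later related SAEs reported under Appendix I, section 4.*

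Baseline data must be named because the serology shift table (SAP 10.3) needs the pre-dose sample. Later related SAEs must be named so that the new text does not itself impose a 28-day limit.

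With that amendment the protocol and SAP agree, and SAP 12 needs no entry on this point. If the protocol is not amended, record in SAP 12 that the cut-off and the adequacy condition of Protocol 10.4 will not be applied, and why. One of the two routes is enough.

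The cost is one sentence in one document. No new data, visits or analyses are needed. The protocol route would go through the amendment procedure in Appendix II, section 6.

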10.5 Demographics and Other Baseline Characteristics

Demographic data, including age, sex, height, weight and ethnic origin will be summarised. These will be displayed in the following age groups:

- ➢ Less than 12 years
- ➢ Greater than and equal to 12 years
- > All subjects

Baseline characteristics, including family history of haemophilia, historical disease data and diagnostic information will be summarised as appropriate.

10.6 Efficacy

All primary and secondary endpoints will be tabulated.

10.6.1 Primary Endpoint

The primary efficacy endpoint is to assess immunogenicity of Optivate[®] by monitoring plasma inhibitor level for at least 100 EDs for each subject.

FVIII inhibitor evaluation

FVIII inhibitor screen data will be listed. FVIII quantitative inhibitor results will be listed. Shift tables will present the number of subjects with positive (≥ 0.6 BU) and negative (< 0.6 BU) results and those for whom the results change during the study. The number of exposure days until development of inhibitors will be summarised.

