7.9.2 FVIII Inhibitors

Both a FVIII inhibitor screen and a quantitative FVIII Nijmegen-Bethesda inhibitor test will be performed at Addenbrooke's Hospital, UK. All inhibitor samples will be collected after a 3 day washout period, when it is anticipated that the pre-substitution FVIII level has reached a nadir¹².

FVIII inhibitor screening test

For the FVIII inhibitor screens, an APTT is performed on a 50/50 mix of a subject's plasma and normal pooled plasma, and compared with the APTT for the subject's plasma and that of normal pooled plasma. A positive inhibitor screen is defined as one that does not correct the APTT by > 50% of the difference between the subject's value and the normal pooled plasma value. To rule out the presence of a time-dependent inhibitor, 50/50 mixes of the subject's plasma and normal plasma are compared following incubation together or separately for 2 hours at 37°C. Time-dependent inhibition is defined as > 4 seconds' prolongation of the incubated mixture relative to the plasmas incubated separately.

FVIII Nijmegen-Bethesda inhibitor test

A Nijmegen-Bethesda assay will also be performed using the same sample as above. A result of ≥ 0.6 BU confirms that the subject has developed inhibitors to FVIII. If this occurs, the test will be repeated on a separate sample; if both tests are confirmed to be ≥ 0.6 BU this will be reported by

the Investigator as an SAE (see Appendix I). The Central Laboratory will notify both the Contract Research Organisation (CRO) and Sponsor immediately if any sample has a value of ≥ 0.6 BU, even if the repeat analysis has not been conducted.

If there is a discrepancy between the FVIII inhibitor screen and Nijmegen-Bethesda assay result, analyses will be repeated on reserve samples and, if necessary, additional samples from the subject, until an unequivocal result, or a reason for the discrepancy, is obtained.

If necessary, repeat FVIII inhibitor quantitative assays will be performed on reserve samples from earlier timepoints, in an attempt to identify the point at which an immune response was initiated. The subject's progress will be monitored closely and if any additional FVIII inhibitor samples are required, these should be taken in triplicate to allow repeat testing and assessment of possible 'transient' inhibitors.

If required, additional methodologies may be used to detect and quantitate inhibitors to FVIII. Any such methodologies will be described in detail in the clinical study report.

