7. GENERAL ASPECTS FOR STATISTICAL ANALYSIS

7.1. GENERAL METHODS

Statistical outputs will be generated using SAS version 9.3 (or later).

The study only has one treatment and so all summary tables will have a single results column for Optivate[®]. However, if subjects suffering from severe haemophilia A with basal FVIII values of < 2% rather than < 1% are recruited into the study, an additional two results columns will be presented, one for subjects with a basal FVIII < 1%, and one for subjects with a basal FVIII $\ge 1\%$ (see Section 6.3).

Continuous variables will be summarised using the number of observations (n), mean, 95% confidence interval for the mean, standard deviation (SD), median, minimum, and maximum. Minima and maxima will be quoted to the number of decimal places as recorded in the CRF, means and medians will be quoted to one further decimal place, and SDs will be quoted to one further decimal place than the mean value. Categorical variables will be summarised using number of observations (n), frequency and percentages of subjects. Percentages will be rounded to one decimal place, with the exception of 0% and 100%, which will be presented to no decimal places.

All relevant subject data will be included in listings. All subjects entered into the database will be included in subject data listings.

Data from unscheduled visits will not be included in the summary tables. These data will be listed only.

Where multiple data/results are available at a given visit for the same parameter, the first non-missing result will be used in the summary tables. All data will however be listed.

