9. EFFICACY

9.1. PRIMARY EFFICACY ENDPOINT AND ANALYSIS

The primary efficacy endpoint is the assessment of immunogenicity of Optivate® by monitoring plasma inhibitor levels for at least 100 EDs for each subject.

Pre-bolus blood samples for quantitative assays will be collected at the Screening Visit, Baseline Visit (Visit 1), Visit 2, Visit 3, the End of Study Visit (Visit 4) and possibly also at unscheduled visits if deemed necessary.

Inhibitor screen data will be listed only.

Quantitative inhibitor results will be listed.

Summaries of quantitative inhibitor levels will be based on both the Per Protocol and Safety populations.

At each visit, the number and percentage of subjects with positive (\geq 0.6 Bethesda Units) and negative (< 0.6 Bethesda Units) results will be summarised.

Shift tables cross tabulating positive/negative status (based on the Bethesda assay) at the Baseline Visit against those at Visits 2, 3 and 4 will be presented. Shifts from the Baseline Visit to any unscheduled visits will also be summarized. Note, should a subject have more than one unscheduled visit then the worst case assessment (positive) will be used in the summary.

The number of exposure days until development of inhibitors (positive status) will be summarized.

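### When a visit's inhibitor screen and Bethesda assay disagree, SAP 7.1 can leave that visit tabulated as negative after a reserve-sample re-assay at 0.6 BU or above

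*Protocol*

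**What the plan says.** Protocol 7.9.2 runs two tests on the same sample: an APTT mixing screen, with an incubation step for time-dependent inhibition, and the Nijmegen-Bethesda assay. On disagreement it says: "If there is a discrepancy between the FVIII inhibitor screen and Nijmegen-Bethesda assay result, analyses will be repeated on reserve samples". New samples follow if necessary, and the work-up continues "until an unequivocal result, or a reason for the discrepancy, is obtained". Protocol 7.9.3 stores reserve plasma for this purpose, among others.

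Protocol 10.6.1 reads: "FVIII inhibitor screen data will be listed. FVIII quantitative inhibitor results will be listed. Shift tables will present the number of subjects with positive" (0.6 BU or above) "and negative (< 0.6 BU) results and those for whom the results change during the study". SAP 9.1 follows: "Inhibitor screen data will be listed only", and it plans "Shift tables cross tabulating positive/negative status (based on the Bethesda assay) at the Baseline Visit against those at Visits 2, 3 and 4". The per-visit counts use the same cut-off, and exposure days until positive status are summarised.

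For several results on one parameter at one visit, SAP 7.1 says that "the first non-missing result will be used in the summary tables", with all data listed. Neither document says that a result settled under Protocol 7.9.2 replaces the initial one in the tables, or how a visit that is still discordant should be shown.

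**The concern.** The laboratory section and the tabulation rule treat the initial Bethesda value differently. Protocol 7.9.2 regards it as provisional when the screen conflicts with it. SAP 7.1 makes it final for the tables. The reserve aliquot exists to settle such conflicts, and its result is the one the tabulation rule would set aside.

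The primary objective is to find out whether any of about ten subjects develops an inhibitor. The tables concerned are the primary ones (SAP Tables 14.2.1.1 to 14.2.1.6). One wrong cell could put the headline table at odds with the listing and the safety section. It could also affect the exposure-day summary, either by omitting the subject or by dating onset from a later visit.

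**Working it through.** There is no planned power, alpha or interval to reproduce. Protocol 10.8 states that no formal sample size calculation was made and that ten evaluable subjects were agreed with the regulator. The check is therefore one of logic.

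**Inputs**
- Positive means a Bethesda value of 0.6 BU or above; negative means below (Protocol 10.6.1, SAP 9.1).
- Screen and Bethesda disagree: re-assay until settled (Protocol 7.9.2).
- Several results at one visit: the first non-missing one is tabulated (SAP 7.1).
- Ten evaluable subjects, 12 to be enrolled (Protocol 10.8).

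**Step 1: apply the rules to each discordant pattern.** The values 0.4 and 0.7 BU are illustrative. The re-assay is assumed to be on the same visit's reserve aliquot and recorded under that visit.

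| Screen | Initial Bethesda | Re-assay | Tabulated status | Compared with the work-up |
|---|---|---|---|---|
| Positive | 0.4 | none yet | Negative | Still open |
| Positive | 0.4 | 0.4 | Negative | Agrees, if accepted as unequivocal |
| Positive | 0.4 | 0.7 | Negative | Conflicts, if 0.7 is accepted |
| Negative | 0.7 | none yet | Positive | Still open |
| Negative | 0.7 | 0.4 | Positive | Conflicts, if 0.4 is accepted |
| Negative | 0.7 | 0.7 | Positive | Agrees |

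The tabulated status depends only on the initial value. The third row is the case at issue. The fifth shows that the same rule can also err in the other direction.

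**Step 2: effect on the exposure-day summary.** Suppose the settled positive belongs to V2 (estimated 10 to 15 EDs), the V2 cell stays negative, and V3 (estimated 50 to 75 EDs) is the first visit tabulated as positive. If the summary follows tabulated status, onset is dated late by between 50 − 15 = 35 and 75 − 10 = 65 EDs. If no later scheduled visit is tabulated as positive, the subject may be left out. The documents do not say which result triggers positive status for this summary, so the effect is possible rather than certain.

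**Step 3: scale of one subject (illustration only).** Exact (Clopper-Pearson) 95% limits:
- 0/10: upper limit = 1 − 0.025^(1/10) = 30.8%, so 0 to 30.8%.
- 1/10: lower limit = 1 − 0.975^(1/10) = 0.25%; upper limit = 97.5th percentile of Beta(2, 9) = 44.5%.
- With 12 subjects: 0/12 gives 0 to 26.5%, and 1/12 gives 0.2 to 38.5%.

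The plan does not call for an interval on the inhibitor proportion. These figures show only how much one subject matters at this size.

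**The case against.** The strongest reply is that status based on Bethesda alone is the protocol's own definition. Protocol 5.3 and 7.2.1 use the 0.6 BU cut-off for eligibility, 7.9.2 treats 0.6 BU or above as confirming an inhibitor, and 10.6.1 and SAP 9.1 carry it into the tables. The APTT test is a screen and never defines status. This stands. A reader might infer that leaving the screen out of the classification is itself an error; the documents do not support that. A screen-positive visit that the work-up settles as negative is correctly tabulated as negative.

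The second reply is that a real inhibitor would be seen elsewhere, and this largely stands too. Screen and quantitative results are both listed (SAP Listing 18), and a listing for ten to twelve subjects can be read line by line. New samples taken at unscheduled visits enter a shift summary that uses the worst case (SAP 9.1). Inhibitor development is automatically serious (Protocol Appendix I, 1.3; SAP 5.3), so a confirmed case is reported as a serious adverse event. None of this corrects the scheduled-visit cell.

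Third, the failure needs several conditions together: a positive screen, an initial value below 0.6 BU, a same-visit re-assay at or above it, and that re-assay recorded under the same visit and parameter. The documents do not say how re-assays are recorded. This limits how often the problem can arise, but does not remove the conflict between the two rules.

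A reader might also infer a general bias of the primary result toward zero. That goes too far, because the opposite discordance is tabulated as positive. Nor can a probability of a missed case be given: the documents state no discordance rate, and any assumed rate would give the chance of a discordant sample, not of a missed inhibitor.

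**Conclusion.** The point holds in a narrow form. Under the rules as written, a scheduled visit can remain negative in the primary status and shift tables after the protocol's own work-up has produced a Bethesda value of 0.6 BU or above. The exposure-day summary could be affected as well. This assumes that the re-assay is recorded under the same visit as the same parameter. If the laboratory transferred only the final accepted value, the problem would not arise, but neither document says that it does.

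The size is at most one cell, and possibly one subject, in a study of about ten; how often is unknown. The error would leave the primary tables inconsistent with the listing and the serious adverse event report, but would not hide a confirmed inhibitor from the study report. A reader might go further and count every unresolved discordant visit as positive. That would conflict with the 0.6 BU definition in both documents and is not supported.

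**What to change.** In SAP 9.1, state that inhibitor status at each scheduled visit is taken from the final Bethesda result accepted after the Protocol 7.9.2 work-up, and that the exposure-day summary uses the same status. In SAP 7.1, exempt inhibitor re-assays from the first-non-missing rule. This also corrects the opposite discordance.

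Show any visit still discordant at database lock, with no documented resolution, in a separate row or footnote labelled unresolved. Because Protocol 7.9.2 requires the work-up to be completed, this should be rare or empty. Keep 0.6 BU on the Bethesda assay as the definition of positive, and do not count unresolved visits as positive.

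The cost is a few sentences of SAP text and one row or footnote in the inhibitor tables. No new data are needed, though re-assay results and the accepted result must be identifiable in the database.
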